### **3.2 Purpose of the Analysis**

This analysis will assess capability of MSOT in comparison to the gold standard (angiography) and the clinical PAD stage as a reference standard to predict the severity of PAD. If necessary, the angiographic findings will be combined with the CCDS measures in order to define a flow relevant stenosis.

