#### *Primary objectives:*

- Study group 1: Derivation of optimal diagnostic MSOT thresholds for hemoglobin through correlation with TASC classification for angiographic imaging (and CCDS if necessary) as references for relevant stenosis/occlusion in patients with PAD.

---

 Angiographic images are reviewed by two independent and experienced individuals to determine the type of TASC.

In the TASC classification for angiographic imaging, the pelvic and femoral arteries are assessed separately based on the extent and localization of the present stenoses/occlusions. However, the perfusion situation in the target region (calf muscle), that is measured by MSOT, results from a combination of both findings. In order to represent the circulation situation in the target muscle properly and to enable a correlation with the MSOT parameters measured there, it is necessary to regard the existing aorto-iliac and femoro-popliteal constellations of findings. For this purpose, 3 categories are established (1 – 3), that result from the occurring combinations of findings of both TASC classifications. The description of the categories can be found in the Statistical Analysis Plan (version 1.1, 01/20/2022).

- Study group 2: Validation of the diagnostic accuracy of MSOT, employing the cut-off values derived in study group 1, in terms of MSOT hemoglobin values through correlation with TASC classification for angiographic imaging as a reference of relevant stenosis/occlusion in patients with PAD in an independent cohort.

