### 4.2 Objectives

#### Primary objectives

- Study group 1: Derivation of optimal diagnostic MSOT thresholds for hemoglobin through correlation with TASC classification for angiographic imaging (and CCDS if necessary) as references for relevant stenosis/occlusion in patients with PAD
- Study group 2: Validation of the diagnostic accuracy of MSOT, employing the cut-off values derived in study group 1, in terms of MSOT hemoglobin values through correlation with TASC classification for angiographic imaging as a reference for relevant stenosis/occlusion in patients with PAD in an independent cohort

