- *individuals with unremarkable radiological findings according to TASC in each of the aortoiliacal (AI), femoropopliteal (FP) and infrapopliteal (IP) levels*

aTASC 2: aTASC type with good chances for collateralization:

- *due to mild findings in AI levels and any findings in FP levels which is considered a potential for collaterals through A. profunda branches.*

aTASC 3: aTASC type with poor chances for collateralization:

- *all combination of AI and FP TASC patterns with theoretically poor chances for collateralization. Here severe findings at AI level are summarized because of poor collateralization capability via A. profunda branches.*

aTASC 1	aTASC 2	aTASC 3
combination of 1. no AI TASC findings 2. no FP TASC findings 3. no IP TASC findings	combination of 1. AI no TASC or TASC A/B 2. FP no TASC or TASC A/B/C/D 3. any IP TASC findings 4. at least TASC A/B in 1. or 2.	combination of 1. AI TASC C/D 2. FP no TASC or TASC A/B/C/D 3. any IP TASC findings

CCDS 	X	Whether a flow-relevant stenosis is present in the examined vessels is decided by an independent reader
ABI 	X	
Clinical scores 	X	

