**CCDS:**

Morphological flow profile and PSV of CFA and A. poplitea

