### 7.3 Subgroups

Subpopulations are defined the reference standard as follows: clinical according to Fontaine and TASC classification (and if necessary and in order to confirm a flow relevant stenosis CCDS).

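### The reference standard for the MSOT threshold is not fixed, and is not stated to be the same for derivation (study group 1) and validation (study group 2)

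*SAP*

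**What the plan says.** The two primary objectives describe the reference differently. For study group 1, SAP 4.2 derives thresholds against the TASC classification "for angiographic imaging (and CCDS if necessary) as references for relevant stenosis/occlusion in patients with PAD". For study group 2 it validates them "through correlation with TASC classification for angiographic imaging as a reference for relevant stenosis/occlusion in patients with PAD in an independent cohort", with no CCDS clause. Protocol 5.1 has the same asymmetry; its study group 2 objective reads "through correlation with TASC classification for angiographic imaging as a reference of relevant stenosis/occlusion in patients with PAD in an independent cohort".

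Two other sections allow CCDS without limiting it to one study group. SAP 3.2 states: "If necessary, the angiographic findings will be combined with the CCDS measures in order to define a flow relevant stenosis". SAP 7.3 defines subgroups by Fontaine stage and TASC, adding "and if necessary and in order to confirm a flow relevant stenosis CCDS".

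On CCDS itself, SAP 5.4 lists what is recorded ("Morphological flow profile and PSV of CFA and A. poplitea") and leaves the call to judgement: "Whether a flow-relevant stenosis is present in the examined vessels is decided by an independent reader". The aTASC classes in SAP 5.4 give CCDS no role for patients. It enters only for volunteers without angiography, who are placed in aTASC 1 on history, ABI and CCDS.

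SAP 9.3 is the only section that says how the cutpoint is obtained. It maximises the Youden index in study group 1, using controls against PAD classes III/IV, and carries that cutpoint to study group 2.

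**The concern.** A validation cohort tests a threshold fairly only if the target condition is defined as it was in derivation. If the definition moves between the two cohorts, estimated sensitivity and specificity change for reasons unrelated to MSOT, and the reader cannot separate that change from ordinary optimism in the derived cutpoint.

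The optional use of CCDS adds a second problem. No finding triggers it, so whether to use it can be decided at the study group 1 analysis, where the cutpoint is being optimised.

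CCDS is also not a neutral tie-breaker here. It examines two arteries, whereas the split between aTASC 2 and aTASC 3 turns on the aorto-iliac level, which CCDS does not image directly in this study. Protocol 2 and SAP 3.1 themselves say that CCDS is among the methods giving inadequate results in some patients, for example those with diabetes or terminal renal failure. MSOT is meant to serve those patients.

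**Working it through.** **Step 1. The reference, place by place.**

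| Place | Study group 1 | Study group 2 |
|---|---|---|
| Protocol 5.1 and SAP 4.2 | TASC angiography, CCDS optional | TASC angiography, CCDS not mentioned |
| SAP 3.2 | Angiography and clinical stage, CCDS optional | Not distinguished from group 1 |
| SAP 7.3 | Fontaine and TASC, CCDS optional | Not distinguished from group 1 |
| SAP 5.4 | aTASC 1 to 3, no CCDS for patients | Not distinguished from group 1 |
| SAP 9.3 | Controls vs. PAD III/IV | Cutpoint carried over, reference not named |

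Three candidate references result: TASC alone, TASC modified by CCDS, and clinical stage. The sample tables in SAP 12.5 to 12.7 plan sensitivity and specificity for Fontaine, Rutherford, combined TASC and CCDS groupings in turn, and mark none as primary.

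**Step 2. Is the optional clause governed by a rule?** A rule would need a trigger, a criterion for a positive CCDS, and a way of combining it with TASC (add positives, remove them, or both). None is given. SAP 7.3 suggests a confirming role, which would mainly remove positives.

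**Step 3. The plan's own figures.** SAP 6 gives about 33 subjects per group for deoxygenated and about 11 for oxygenated hemoglobin (80% power, one-sided alpha 0.05). No mean difference or standard deviation is stated, so these numbers cannot be reproduced. Inverting the normal two-sample formula gives the standardised differences they imply:

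- d = √2 × (1.645 + 0.842) / √n
- n = 33: d = 0.61
- n = 11: d = 1.06

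The t-test versions are 0.62 and 1.10. These values serve below only as plausible separations. They come from healthy subjects against stages III and IV, so separation for all angiography positives could be smaller.

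**Step 4. Illustration of a reference switch.** All of the following are assumptions; none is in the documents.

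- The readout is normal with equal variance, with controls at 0 and CCDS-confirmed positives at d.
- The cutpoint is the Youden optimum d/2, derived from confirmed positives against controls.
- Validation uses all angiography positives, a share f of which CCDS would not confirm.
- Unconfirmed cases lie at m × d, with m = 0 (like controls) or m = 0.5 (halfway).

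In derivation, sensitivity = specificity = Φ(d/2), which is 0.702 for d = 1.06 and 0.620 for d = 0.61. In validation:

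sensitivity = (1 − f) × Φ(d/2) + f × [1 − Φ(d/2 − m·d)]

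The bracket is 0.298 (d = 1.06) or 0.380 (d = 0.61) when m = 0, and 0.500 when m = 0.5. For d = 1.06, f = 0.30 and m = 0: 0.70 × 0.702 + 0.30 × 0.298 = 0.581.

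| f | d = 1.06, m = 0 | d = 1.06, m = 0.5 | d = 0.61, m = 0 | d = 0.61, m = 0.5 |
|---|---|---|---|---|
| 0% | 70% | 70% | 62% | 62% |
| 10% | 66% | 68% | 60% | 61% |
| 20% | 62% | 66% | 57% | 60% |
| 30% | 58% | 64% | 55% | 58% |

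The largest loss is 70.2 − 58.1 = 12.1 points. Specificity does not move, because the classification of controls does not change.

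**The case against.** The strongest reply is that SAP 9.3 is the operative rule. It takes clinical stages III and IV as cases, and CCDS does not define those. Under that rule no threshold is tuned to angiography plus CCDS at all. This stands, and it limits the point: the illustration in step 4 applies only if the threshold is derived as the SAP 4.2 objective describes. It does not restore a single reference, though. SAP 9.3 then conflicts with the TASC reference in SAP 4.2 and still leaves study group 2 unnamed.

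Second, the asymmetry rests on a parenthesis that one objective has and the other lacks, while SAP 3.2 and 7.3 fit the same reference in both groups equally well. A reader might infer that the plan has settled on angiography plus CCDS for derivation and angiography alone for validation. The documents do not support that. They support a reference that can differ, and that conflicting sections leave open.

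Third, SAP 5.3 blinds angiography and CCDS investigators to MSOT, and the MSOT reader to TASC and CCDS; two independent readers assign TASC. This answers the worry about biased readings. It does not say who decides that CCDS is needed, or when.

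Fourth, using duplex to confirm flow relevance is a defensible reference, so one written rule applied equally would also close the gap. That is fair. Angiography alone is preferred because it is already the stated reference for study group 2 and removes the discretionary step. That CCDS is also a secondary correlate of MSOT is no defect in itself, since TASC is one too.

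**Conclusion.** The concern holds as a failure to fix one reference for derivation and validation, with CCDS as one source of the mismatch and the clinical-stage contrast in SAP 9.3 as another. It bears on the primary validation claim and should be corrected, but its effect depends on how the optional clause is used.

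The documents give no disagreement rate between angiography and CCDS, so the loss cannot be computed from them. On the one-way model above, with 0 to 30% of angiography positives unconfirmed, it is 0 to about 12 points of sensitivity and none of specificity. A mismatch between clinical-stage derivation and TASC validation cannot be sized at all from what is given.

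A reader might infer a larger loss in both sensitivity and specificity by assuming symmetric disagreement with half the limbs diseased. The documents do not support that model. SAP 7.3 gives CCDS a confirming role, and volunteers without angiography are already classified partly by CCDS. SAP 5.2 expects similar sizes for controls and four patient groups, so about 4/5 = 80% would be patients.

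**What to change.** Amend SAP 3.2, 4.2, 7.3 and 9.3 and protocol 5.1 together, so that no section contradicts another:

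- State one primary reference for both study groups: the angiographic aTASC class, with volunteers without angiography classified as in SAP 5.4.
- State which aTASC classes count as positive and which as negative, before study group 2 is analysed. With three classes, sensitivity and specificity are undefined until this is done.
- Delete the if-necessary clause wherever it qualifies the reference.
- Run angiography plus CCDS as a sensitivity analysis under one written rule (trigger, CCDS criterion, way of combining with TASC), applied the same way in both groups.
- Either align the SAP 9.3 contrast with the primary reference, or label it a separate clinical-stage analysis and validate it on the same contrast in study group 2.

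The cost is SAP and protocol wording and one extra analysis. No new patients, data or procedures are needed.

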## 4 Hypothesis, Study Objectives and Endpoints

### 4.1 Hypothesis to be statistically tested

The hypothesis is that MSOT can predict clinical and angiographic disease severity in patients with PAD.

- H0: MSOT parameters are not associated with angiographic manifestations
- H0: MSOT parameters do not differ between healthy subjects and patients with PAD (graded according to angiographic classifications)

### 4.2 Objectives

#### Primary objectives

- Study group 1: Derivation of optimal diagnostic MSOT thresholds for hemoglobin through correlation with TASC classification for angiographic imaging (and CCDS if necessary) as references for relevant stenosis/occlusion in patients with PAD
- Study group 2: Validation of the diagnostic accuracy of MSOT, employing the cut-off values derived in study group 1, in terms of MSOT hemoglobin values through correlation with TASC classification for angiographic imaging as a reference for relevant stenosis/occlusion in patients with PAD in an independent cohort

#### Secondary objectives

- Determination of the quantitative fraction of oxygenated/deoxygenated/total hemoglobin and the MSOT-values at a wavelength of 800 nm in the area of the TS before and after gait exposure determined by MSOT
- Correlation of the quantitative fraction of oxygenated/deoxygenated/total hemoglobin and the MSOT-values at a wavelength of 800 nm in the area of the TS determined by MSOT with the TASC-classification in angiography
- Comparison of the difference between oxygenated and deoxygenated hemoglobin in the area of the TS before and after gait exposure determined by MSOT
- Correlation of the difference between oxygenated and deoxygenated hemoglobin in the area of the TS before and after gait exposure determined by MSOT with the TASCclassification in angiography

---

 Angiographic images are reviewed by two independent and experienced individuals to determine the type of TASC.

- Determination of the quantitative lipid/collagen signal fraction and the MSOT-values at a wavelength of 930 and 1064 nm determined by MSOT
- Correlation of the flow profile and PSV of the CFA and A. poplitea determined by CCDS with the acquired MSOT parameters
- Correlation of the ABI with the acquired MSOT parameters  
Correlation of the walking distance determined by treadmill examination with the acquired MSOT parameters
- Correlation of the clinical severity of PAD according to the Fontaine and Rutherford classifications with the acquired MSOT parameters

### 4.3 Endpoints

#### Primary endpoint

- Optimal diagnostic MSOT thresholds [Time Frame: single time point (1 day)]: Optimal diagnostic thresholds for hemoglobin values in muscle tissue determined by MSOT in patients with PAD

#### Secondary endpoints

- Muscular oxygenated/deoxygenated/total hemoglobin content and MSOT-values at a wavelength of 800 nm before and after gait exposure [Time Frame: single time point (1 day)]: Quantitative oxygenated/deoxygenated/total hemoglobin signal and signal at a wavelength of 800 nm (Units: arbitrary units (a. u.)) derived by transcutaneous MSOT in patients with PAD before gait exposure compared to the signals after gait exposure
- Correlation of oxygenated/deoxygenated/total hemoglobin content and MSOT-values at a wavelength of 800 nm with the TASC-classification (angiography) [Time Frame: single time point (1 day)]: Quantitative oxygenated/deoxygenated/total hemoglobin signal and signal at a wavelength of 800 nm (Units: arbitrary units (a. u.)) derived by transcutaneous MSOT in patients with PAD correlated with the TASC-classification (angiography)
- Difference between oxygenated/deoxygenated hemoglobin before and after gait exposure [Time Frame: single time point (1 day)]: Difference between quantitative oxygenated hemoglobin amount (Units: arbitrary units (a. u.)) and quantitative deoxygenated hemoglobin amount (Units: arbitrary units (a. u.)) derived by transcutaneous MSOT in patients with PAD before gait exposure compared to the amount after gait exposure
- Correlation of difference between oxygenated/deoxygenated hemoglobin with the TASC-classification (angiography) [Time Frame: single time point (1 day)]: Difference between quantitative oxygenated hemoglobin amount (Units: arbitrary units (a. u.)) and

quantitative deoxygenated hemoglobin amount (Units: arbitrary units (a. u.)) derived by transcutaneous MSOT in patients with PAD correlated with the TASC-classification (angiography)

Muscular quantitative lipid/collagen signal fraction and the MSOT-values at a wavelength of 930 and 1064 nm [Time Frame: single time point (1 day)]: Quantitative lipid/collagen signals and signals at 930 and 1064 nm (Units: arbitrary units (a. u.)) derived by transcutaneous MSOT in patients with different clinical and angiographic PAD stages

- Correlation of acquired MSOT parameters with the CCDS flow profile and PSV [Time Frame: single time point (1 day)]: Quantitative oxygenated/deoxygenated/total hemoglobin content and MSOT-values at a wavelength of 800 nm (Units: arbitrary units (a. u.)) derived by transcutaneous MSOT in patients with PAD correlated with the flow profile and PSV of A. CFA and A. poplitea determined by CCDS
- Correlation of acquired MSOT parameters with the ABI [ Time Frame: single time point (1 day)]: Quantitative oxygenated/deoxygenated/total hemoglobin content and MSOTvalues at a wavelength of 800 nm (Units: arbitrary units (a. u.)) derived by transcutaneous MSOT correlated with the ABI
- Correlation of acquired MSOT parameters with the walking distance determined by treadmill examination [ Time Frame: single time point (1 day)]: Quantitative oxygenated/deoxygenated/total hemoglobin content and MSOT-values at a wavelength of 800 nm (Units: arbitrary units (a. u.)) derived by transcutaneous MSOT correlated with the walking distance determined by treadmill examination
- Correlation of acquired MSOT parameters with the clinical severity of PAD [ Time Frame: single time point (1 day)]: Quantitative oxygenated/deoxygenated/total hemoglobin content and MSOT-values at a wavelength of 800 nm (Units: arbitrary units (a. u.)) derived by transcutaneous MSOT correlated with the clinical severity of PAD according to Fontaine and Rutherford

## 5 Study Methods

### 5.1 General Study Design and Plan

This is a monocentric, prospective cross-sectional study which aims to compare the optoacoustic signals in patients with different PAD stages with TASC-classification in angiographic imaging in order to define thresholds for MSOT in these patients. MSOT data will be correlated with clinical disease severity (Fontaine; Rutherford; walking distance; ABI), CCDS and TASC II classification in angiographic imaging.

Patients with PAD will be recruited from the consulting hour of the Department of Vascular Surgery, University Hospital Erlangen. Healthy volunteers will be acquired via posters in the clinic. Following careful information about the study and after providing written consent, relevant clinical data will be collected from the electronical patient file, if available. Otherwise an anamnesis interview for relevant data is performed. The CCDS, ABI and measurement of the walking distance will be performed. Afterwards the MSOT parameters will be collected before and after an active gait exposure. If it is reasonable, both sides will be examined for all participants. The focus, however, is on the more affected leg. All data will be adequately pseudonymized in compliance with data protection regulations before they are used for statistical analysis. The duration of the study for participants will be approx. 1.5 hours. Angiographic imaging will be reviewed and analyzed if the interval between index test and angiography is less than 12 months. The complete study including the validation of the data by an independent study group is expected to be finished within one year.

## 5.2 Study Population

At the moment we anticipate a number of approx. 200 subjects in total. We also anticipate similar group sizes for healthy control group and the four groups of PAD patients. Age should be similar in all investigated groups.

### ***Definition of patient groups:***

- PAD IIa with indication for angiography
- PAD IIb with indication for angiography
- PAD III with indication for angiography
- PAD IV with indication for angiography

### ***Definition of healthy control group:***

- No PAD previously known
- No diabetes mellitus previously known
- No chronic renal insufficiency previously known
- No symptoms in the sense of a Claudicatio intermittens
- ABI with values between 1.0 and 1.4

### **Inclusion Criteria**

- Patients with manifest PAD stages II – IV according to Fontaine or category 1-6 according to Rutherford or healthy volunteer
- Adult (>18 years) persons who are able to give their consent

- Patients with manifest PAD in whom angiography has been performed as part of routine diagnostics (independent of the study) or in accordance with current guidelines, or has been indicated and the patient has given consent; healthy volunteers do not need a previous performed angiography

## Exclusion Criteria

- Patients with PAD stage I according to Fontaine or category 0 according to Rutherford
- Healthy volunteers with previous known diabetes mellitus or chronic renal insufficiency or abnormal ABI
- Underage persons
- Missing consent form
- Patients with manifest PAD in whom angiography is not indicated
- Exclusion due to safety concerns of the study physician (patient with a physical, mental or psychiatric illness which, in the opinion of the study physician, would compromise the safety of the patient or the quality of the data and thus make the patient an unsuitable candidate for the study)

## 5.3 Randomization and Blinding

Randomization is not applicable in the chosen study design. Investigators for angiography and CCDS are blinded to index test (MSOT) results. An independent reader blinded to angiographic TASC-classification and CCDS measures performs data analysis for index test (MSOT).

## 5.4 Study Variables

	Visit	Annotations
Index test (MSOT) 	X	Before and after gait exposure
Angiography 		Less than 12 months to the date of index test was considered for statistical analysis, from electronic patient file by two independent readers

###  Index Test (MSOT):

Signal levels for oxygenated hemoglobin (HbO2), deoxygenated hemoglobin (Hb), collagen and lipids in arbitrary units (a.u.)

###  Angiography:

TASC II classification femoro-popliteal PAD:  
Type-A:

- *circumscribed stenosis ≤ 10 cm or closure ≤ 5 cm length Type-B:*
- *several hemodynamically relevant findings (stenoses or occlusions), each ≤ 5 cm*
- *single stenosis or occlusion ≤ 15 cm length, not involving the infrageniculate popliteal artery*
- *single or multiple findings in peripheral vascular occlusion to improve inflow for distal bypass*
- *heavily calcified occlusion ≤ 5 cm length*

- *single popliteal stenosis Type-C:*
- *multiple stenoses or occlusions with a total  $\geq 15$  cm vessel involvement, with or without severe calcification*
- *Recurrent stenoses or occlusions requiring treatment after two endovascular interventions*
- Type-D:
  - *chronic total occlusion of the CFA or the SFA (>20 cm) with affection of the arteria poplitea*
  - *chronic complete occlusion of the popliteal artery and proximal trifurcation*

TASC II classification aorto-iliac PAD: Type-A:

- *uni-/bilateral stenoses of CIA*
- *uni-/bilateral single stenosis  $\leq 3$  cm of EIA* Type-B:
  - *$\leq 3$  cm stenosis of infrarenal aorta*
  - *unilateral CIA occlusion*
  - *single or multiple stenosis totaling 3-10 cm involving the EIA but not extending into CFA*
  - *unilateral EIA occlusion not involving IIA or CFA* Type-C:
    - *bilateral CIA occlusions*
    - *bilateral EIA stenoses 3-10 cm long but not extending into CFA*
    - *unilateral EIA stenosis extending into CFA*
    - *unilateral EIA occlusion that involves the IIA and/or CFA*
    - *heavily calcified unilateral EIA occlusion with or without involving IIA and/or CFA* Type-D:
      - *infrarenal aortoiliacal occlusion*
      - *diffuse disease involving aorta and both CIA requiring treatment*
      - *diffuse multiple stenoses involving unilateral CIA, EIA and CFA*
      - *Unilateral occlusion of both CIA and EIA*
      - *bilateral occlusion of EIA*
      - *iliac stenoses with AAA requiring treatment (not amenable to endograft placement or other lesions requiring open aortic/iliac surgery*

Formed subgroups (aggregated TASC [aTASC]) combining TASC types according to severity and theoretically collateralization capability

aTASC 1: Healthy aTASC Type:

- *In the absence of angiographic imaging in the HV and otherwise normal findings in the medical history, ABI, and CCDS, HV are classified as aTASC 1*
- *individuals with unremarkable radiological findings according to TASC in each of the aortoiliacal (AI), femoropopliteal (FP) and infrapopliteal (IP) levels*

aTASC 2: aTASC type with good chances for collateralization:

- *due to mild findings in AI levels and any findings in FP levels which is considered a potential for collaterals through A. profunda branches.*

aTASC 3: aTASC type with poor chances for collateralization:

- *all combination of AI and FP TASC patterns with theoretically poor chances for collateralization. Here severe findings at AI level are summarized because of poor collateralization capability via A. profunda branches.*

aTASC 1	aTASC 2	aTASC 3
combination of 1. no AI TASC findings 2. no FP TASC findings 3. no IP TASC findings	combination of 1. AI no TASC or TASC A/B 2. FP no TASC or TASC A/B/C/D 3. any IP TASC findings 4. at least TASC A/B in 1. or 2.	combination of 1. AI TASC C/D 2. FP no TASC or TASC A/B/C/D 3. any IP TASC findings

CCDS 	X	Whether a flow-relevant stenosis is present in the examined vessels is decided by an independent reader
ABI 	X	
Clinical scores 	X	

